### **Urinalysis / urinalysis microscopic evaluation, hormonal tests, serum, serology, cancer antigen 19.9**

All test results for urinalysis /urinalysis microscopic evaluation, hormonal tests, serum and serology parameters will also be listed in dedicated listings:

- Urinalysis parameters:
  - Urinalysis full parameters: physical appearance, pH, specific gravity, protein, glucose, ketones, nitrite, leukocyte esterase, blood, urobilinogen, bilirubin, color
  - Urinalysis microscopic parameters: erythrocytes (RBC), leukocytes (WBC), epithelial cells, bacteria, crystals, casts, mucus
- Hormonal parameters: thyroxine free (Free T4), thyrotropin (Thyroid-Stimulating Hormone; TSH)
- Serum parameters: Krebs von den Lungen-6 (KL-6), surfactant protein A (SP-A), surfactant protein D (SP-D) (only for Japanese sites)
- Cancer antigen 19.9
- Serology parameters: hepatitis B virus (HBV), hepatitis C virus (HCV), hepatitis B DNA, hepatitis C RNA

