#### **6.9.2 Immune-Related Adverse Events**

In general, the spectrum of irAEs is similar for M7824 compared with other checkpoint inhibitors. Immune-related AEs are considered AESIs. Effective risk management of these toxicities (irAEs) primarily caused due to inhibition of PD-L1 and PD-1 pathways is based on key recommendations ([Champiat 2016](#)). Participant education for on-time reporting of symptoms of potential irAEs and prompt clinical assessment is critical for effective management and quicker resolution of immune-mediated toxicities, thus preventing progression into severe forms of toxicity that otherwise may become life-threatening and difficult to manage or warrant permanent discontinuation from the study.

Immune-related AEs are specific to immunotherapies and vary by organ system.

The following immune-related AEs are important identified risks for M7824:

- Immune-related hepatitis
- Immune-related pneumonitis
- Immune-related colitis

- Immune-related nephritis and renal dysfunction
- Immune-related endocrinopathies (thyroid disorders, adrenal insufficiency, Type 1 diabetes mellitus, pituitary disorders)
- Immune-related rash
- Other immune-related events (myositis, myocarditis, encephalitis)

The following irAEs are important potential risks for M7824:

- Guillain-Barré syndrome
- Uveitis
- Pancreatitis
- Myasthenia gravis/myasthenic syndrome

The Medical Monitor may be involved as needed for follow-up. Details of the diagnostic work-up will be requested by the study team.

For treatment management of irAEs per NCI-CTCAE v5.0 criteria, refer to the ASCO Clinical Practice Guidelines and National Comprehensive Cancer Network (NCCN) irAE management guidelines.

The recommendations for irAE management are guided by the joint ASCO Clinical Practice Guidelines (Brahmer 2018) and NCCN guidelines, listed in [Appendix 6](#).

Treatment of irAEs is mainly dependent upon severity as defined by NCI-CTCAE v5.0. In general, management by NCI-CTCAE v5.0 grading, as per ASCO, is listed below:

- Grade 1: study intervention should be continued with close monitoring, with the exception of some neurologic, hematologic, and cardiac toxicities.
- Grade 2: study intervention may be suspended for most Grade 2 toxicities, with consideration of resuming when symptoms revert to Grade 1 or less. Corticosteroids may be administered (initial dose of 0.5 to 1 mg/kg/day of prednisone or equivalent).

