## Laboratory Variables

Laboratory results will be classified by grade according to NCI-CTCAE v5.0. The worst on-study grades after the first study intervention will be summarized. Shifts in toxicity grading from first treatment to highest grade will be displayed. Results for variables that are not part of NCI-CTCAE v5.0 will be presented as below, within, or above normal limits. Only participants with postbaseline laboratory values will be included in these analyses.

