### **Abnormal Laboratory Findings and Other Abnormal Investigational Findings**

Abnormal laboratory findings and other abnormal investigational findings (e.g., on an ECG trace) should not be reported as AEs unless they are associated with clinical signs and symptoms, lead to study intervention discontinuation or are considered otherwise medically important by the Investigator. If a laboratory abnormality fulfills these criteria, the identified medical condition (e.g., anemia or increased ALT) must be reported as the AE rather than the abnormal value itself.

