## Changes to the Planned Analyses in the Clinical Study Protocol

The statistical methods as described in the protocol were adopted. There are no changes to the planned analyses.

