### Laboratory parameters with NCI-CTC grades available

Laboratory parameters with NCI-CTC grades available will be analyzed with their respective NCI-CTC name and direction of abnormality. For parameters which are graded with both low and high values as potassium (hypokalemia/hyperkalemia), the toxicities will be summarized separately. Low direction toxicity (e.g. hypokalemia) grades at baseline and post-baseline will be set to 0 when the variables are derived for summarizing high direction toxicity (e.g. hyperkalemia), and vice versa.

The following summaries will be displayed:

- Number and percentage of participants by worst on-treatment grade ( $\geq 1$ ,  $\geq 3$ ,  $\geq 4$ )

- Shift in toxicity grading from baseline to highest on-treatment toxicity grade

The definitions of the NCI-CTCAE toxicity grading version 5.0 for each parameter are provided in [Appendix 3](#) of this IAP.

**Table 7** NCI-CTC Gradable parameters

Parameter	Parameter code	Name in NCI-CTC	Direction of abnormality
Biochemistry			
Alanine Aminotransferase	ALT	Alanine aminotransferase increased	High
Albumin	ALB	Hypoalbuminemia	Low
Alkaline Phosphatase	ALP	Alkaline phosphatase increased	High
Amylase	AMYLASE	Serum amylase increased	High
Aspartate Aminotransferase	AST	Aspartate aminotransferase increased	High
Bilirubin total	BILI	Blood bilirubin increased	High
Calcium a	CA	Hypercalcemia/Hypocalcemia a	High/Low
Creatinine	CREAT	Creatinine increased	High
Glucose	GLUC	Hypoglycemia	Low
Lipase	LIPASET	Lipase increased	High
Potassium	K	Hyperkalemia/Hypokalemia	High/Low
Sodium	SODIUM	Hypernatremia/Hyponatremia	High/Low
Hematology			
Absolute eosinophils	EOS	Eosinophilia	High
Absolute lymphocyte	LYM	Lymphocyte count decreased/Lymphocyte count increased	High/Low
Absolute neutrophils	NEUT	Neutrophil count decreased	Low
Hemoglobin	HGB	Anemia/Hemoglobin increased	Low/High
Leukocytes (WBC)	WBC	Leukocytosis/White blood cell decreased	High/Low
Platelets count	PLAT	Platelet count decreased	Low
Coagulation			
Activated Partial Thromboplastin Time b	APTT	Activated partial thromboplastin time prolonged	High
Activated PTT/Standard b	APTTSTND	Activated partial thromboplastin time prolonged	High
Prothrombin International Normalized Ratio b	INR	INR increased	High

a based on corrected calcium (see [Appendix 3](#))

b reported on the “Coagulation” eCRF page

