### **Laboratory parameters with NCI-CTC grades not available**

**Table 8** Non-NCI-CTC Gradable Parameters

Parameter (LBTEST)	
Biochemistry	
Bilirubin direct	BILIDIR
Bilirubin Indirect	BILINDIR
Chloride	CL
C-Reactive Protein	CRP
Total Protein	PROT
Urea Nitrogen	BUN
Hematology	
Absolute Basophils	BASO
Absolute Monocytes	MONO
Absolute Reticulocytes	RETI
Basophils/Leukocytes	BASOLE
Eosinophils/Leukocytes	EOSLE
Erythrocytes (RBC)	RBC
Hematocrit	HCT
Lymphocytes/Leukocytes	LYMLE
Mean Corpuscular Hemoglobin	MCH
Mean Corpuscular HGB Concentration	MCHC
Mean Corpuscular Volume	MCV
Monocytes/Leukocytes	MONOLE
Neutrophils/Leukocytes	NEUTLE
Reticulocytes/Erythrocytes	RETIRBC
Coagulation	
Prothrombin Time*	PT
Standard Prothrombin Time*	PTS

\* reported on the “Coagulation” eCRF page

For all non-gradable parameters, the following summaries will be displayed:

- Number and percentage of participants by lowest on-treatment value (classified as normal, high, low)

- Number and percentage of participants by highest on-treatment value (classified as normal, high, low)
- Shift from baseline to highest/lowest on-treatment value (classified as normal, high, low)

Separate listings of hematology, biochemistry and coagulation will be created. Each listing will include: participant identifier, age, sex, race, first dose date, last dose date, laboratory parameter (units), visit, date, International System of Units (SI) value, lower limit of normal (LLN), upper limit of normal (ULN), indicator of normal range (low, normal, high), toxicity grade according to NCI-CTCAE (when applicable) and highest/lowest on treatment value flag. Baseline and post-baseline values after the on-treatment period will be flagged. These listings will be sorted by participant identifier, parameter and laboratory measurement date.

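### SAP Tables 7 and 8 specify no participant-level worst-value count or baseline shift for high glucose, TSH or free T4, although thyroid disorders and type 1 diabetes are important identified risks

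*SAP*

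**What the plan says.** Protocol 9.4.2 (Laboratory Variables) sets the general rule: gradable tests are summarized by worst grade and by shift in grade, and for the rest "Results for variables that are not part of NCI-CTCAE v5.0 will be presented as below, within, or above normal limits". The opening of SAP 15.3 repeats that classification and adds by-visit statistics, change from baseline and boxplots.

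SAP 15.3 then becomes specific. Table 7 lists the gradable parameters with the direction of abnormality. The glucose row reads "Glucose GLUC Hypoglycemia Low". Table 7 parameters get counts by worst on-treatment grade and "Shift in toxicity grading from baseline to highest on-treatment toxicity grade". Table 8 lists the non-gradable parameters, and beneath it: "For all non-gradable parameters, the following summaries will be displayed". Those summaries are counts by lowest and by highest on-treatment value, and shifts from baseline, each classed as normal, high or low.

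TSH and free T4 appear further on, under hormonal parameters: "All test results for urinalysis /urinalysis microscopic evaluation, hormonal tests, serum and serology parameters will also be listed in dedicated listings".

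Protocol 6.9.2 counts among the important identified risks "Immune-related endocrinopathies (thyroid disorders, adrenal insufficiency, Type 1 diabetes mellitus, pituitary disorders". On adverse event reporting, Protocol Appendix 4 says that abnormal laboratory findings "should not be reported as AEs unless they are associated with clinical signs and symptoms", lead to discontinuation, or are otherwise judged medically important. SAP 7 states: "There are no changes to the planned analyses".

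**The concern.** The two parameter lists are what a programmer will work from. If a test or a direction is in neither list, the general rule at the head of the section has nothing to act on, and the expected output is a listing. Here that happens for the laboratory signs of two named risks.

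At stake is the question a safety reader asks first: how many participants with normal glucose or thyroid function at baseline became abnormal on treatment? The event tables answer it for cases reported as adverse events. They cannot answer it for cases that Appendix 4 keeps out of event reporting. Liver tests, by contrast, receive threshold counts and eDISH plots in the same section.

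**Working it through.** No arithmetic beyond counting rows applies, so I set the specified outputs side by side.

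**Inputs.** Table 7 has 21 rows (12 biochemistry, 6 hematology, 3 coagulation). Table 8 has 22 (6 biochemistry, 14 hematology, 2 coagulation). In the Protocol, glucose belongs to the chemistry panel (Appendix 5, Table A), drawn every 2 weeks; TSH and free T4 are drawn every 6 weeks (Table 1).

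| Result | Table 7: grade counts and shift | Table 8: low/normal/high counts and shift | By-visit summary | Listing |
|---|---|---|---|---|
| Glucose, low | yes | no | yes | yes |
| Glucose, high | no | no | yes, as distribution only | yes, with normal range and highest-value flag |
| TSH, free T4 | no | no | not named; general rule only | yes, dedicated |

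**Step 1: glucose.** Six Table 7 rows carry both directions (calcium, potassium, sodium, lymphocytes, hemoglobin, leukocytes). Glucose carries one. A participant whose glucose is normal at baseline and later exceeds 250 mg/dL has no hypoglycemia grade at either time and does not register as a change in the grade shift table. Table 8 would show the move from normal to high, but glucose is not in it.

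**Step 2: does the general rule rescue high glucose?** Not clearly. It covers results that are not part of NCI-CTCAE, while Table 7 treats glucose as gradable. High glucose falls between the two routes.

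**Step 3: thyroid tests.** TSH and free T4 are in neither table. As non-graded results they fall under the general rule, but Table 8, the list that carries the rule out, stops at biochemistry, hematology and coagulation.

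**Step 4: do the event tables cover the same participants?** Only in part. The immune-related algorithm (SAP 15.2.4.2) needs a pre-selected preferred term and a record that corticosteroid, immunosuppressant or hormonal therapy was given. Protocol Appendix 6 Table A4 describes cases that can miss this: an asymptomatic participant with TSH below 10 mIU/L who is monitored, or hyperthyroidism for which it says steroids are not usually needed. An asymptomatic laboratory change not judged medically important also stays out of the general event tables under Appendix 4.

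**Step 5: do the by-visit statistics substitute?** No. A mean, maximum or boxplot at each visit does not give the number of participants who moved from normal to high at any time on treatment.

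**The case against.** The strongest reply is that the governing text already covers this. SAP 15.3 opens by sending laboratory values to summary statistics and shift tables, exempts no test from low/normal/high classification, and says that hormonal results will *also* be listed, which does not exclude a table. Clinical type 1 diabetes and thyroid disorders are tabulated as immune-related subcategories by worst grade and preferred term (SAP 15.2.4.2), and all treatment-emergent events are tabulated without the therapy filter (SAP 15.1.1). Protocol 8.2.3 tells the investigator to record clinically relevant laboratory changes as adverse events. The grading definitions are in SAP Appendix 3, a separate file not supplied, so low-only grading of glucose may be deliberate.

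Much of this stands. A reader might infer that these risks are never counted in any table; the event tables show otherwise. A reader might also infer an undeclared departure from the protocol. The documents do not support that: SAP 15.3 restates the protocol's rule, and the protocol promises shifts only for toxicity grades, so the statement in SAP 7 is not contradicted by the general text. What remains is that the rule is not carried into the lists that produce output. A deliberate choice about grading would not explain why glucose is missing from Table 8.

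It is also tempting to tabulate glucose by the limits in Appendix 6 Table A4. I would not. The lower limits there are stated for fasting values, the protocol panel requires no fasting, and Table A4 itself notes that corticosteroids can cause or worsen diabetes. Such counts would not identify type 1 diabetes.

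**Conclusion.** The point holds as a specification gap in secondary safety output. Following the parameter lists, high glucose, TSH and free T4 get no participant-level worst-value count and no baseline shift, despite the plan's own general rule and the risk status of the conditions. In size it is three missing rows beside the 22 in Table 8. The documents give no expected frequency of these abnormalities, so the number of participants affected cannot be estimated.

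The uncounted cases are mainly asymptomatic laboratory abnormalities not reported as adverse events. Glucose remains visible in by-visit summaries, and all three tests remain in listings. The primary analysis is untouched.

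The conclusion assumes that programming follows Tables 7 and 8 rather than the opening paragraph, and that the unseen Appendix 3 does not add a high-glucose grade. If it does, Table 7 needs that direction added to match.

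**What to change.** Add glucose (high direction), TSH and free T4 to SAP Table 8, so that each receives the lowest and highest on-treatment classification and the baseline shift table already defined there. Table 8 goes from 22 to 22 + 3 = 25 rows. Keep the hypoglycemia row in Table 7, and footnote that glucose may be non-fasting. If the sponsor intends these tests to be listed only, SAP 15.3 should say so and give the reason.

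The cost is a few rows in existing table programs, with no new data collection. The downside is interpretive: some high glucose values will reflect non-fasting samples or steroid use, so the counts describe laboratory abnormality and are not counts of diabetes.

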### **Pregnancy test**

Results for pregnancy and post-menopausal status as collected on the "Pregnancy Test" and 'FSH and Estradiol' eCRF pages will also be listed:

- Pregnancy parameters (serum or highly sensitive urine human chorionic gonadotropin (hCG))
- Post-menopausal status: FSH and estradiol parameters

## **15.4 Vital Signs**

Summary table over time will present summary statistics for vital signs variables by timepoint.

The following potentially clinically significant abnormalities will be summarized:

- $\leq 95$  mmHg and decrease from baseline  $\geq 20$  mmHg in systolic blood pressure
- $\geq 140$  mmHg and increase from baseline  $\geq 20$  mmHg in systolic blood pressure
- $\leq 45$  mmHg and decrease from baseline  $\geq 20$  mmHg in diastolic blood pressure

- $\geq 90$  mmHg and increase from baseline  $\geq 20$  mmHg in diastolic blood pressure
- $\leq 50$  beats/min and decrease from baseline  $\geq 20$  beats/min in heart rate
- $\geq 100$  beats/min and increase from baseline  $\geq 20$  beats/min in heart rate
- $\leq 20$  breaths/min and decrease from baseline  $\geq 5$  breaths/min in respiratory rate
- $\geq 20$  breaths/min and increase from baseline  $\geq 5$  breaths/min in respiratory rate
- $\geq 10\%$  weight increase
- $\geq 10\%$  weight decrease

A listing of vital signs will be provided including participant identifier, age, sex, race, vital sign parameter, visit, timepoint, date, time, value, unit and change from baseline. Baseline values and post-baseline values collected after the on-treatment period will be flagged.

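### SAP 15.4 uses 20 breaths/min as both the low and the high respiratory-rate limit, so for baselines up to 25 the low criterion is simply any fall of 5 or more

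*SAP*

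**What the plan says.** SAP section 15.4 (Vital Signs) introduces a list with "The following potentially clinically significant abnormalities will be summarized". The entries come in pairs. For four parameters each entry joins an absolute limit to a change from baseline:

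- Systolic pressure: 95 mmHg or less with a fall of at least 20; 140 mmHg or more with a rise of at least 20.
- Diastolic pressure: 45 mmHg or less with a fall of at least 20; 90 mmHg or more with a rise of at least 20.
- Heart rate: 50 beats/min or less with a fall of at least 20; 100 beats/min or more with a rise of at least 20.
- Respiratory rate: at most 20 ("breaths/min and decrease from baseline" of at least 5); at least 20 ("breaths/min and increase from baseline" of at least 5).

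Weight is handled differently: a change of 10% or more in either direction, with no absolute limit. Section 15.4 also plans summary statistics by timepoint and a listing of each value with its change from baseline.

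Protocol section 8.2.1 confirms that respiratory rate is recorded as a vital sign. Neither document gives another low limit for respiratory rate, a normal range, or a reason for using the same number twice.

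**The concern.** In a joint criterion the absolute limit has a job: it keeps a change that ends in the ordinary range from being called an abnormality. With 20 as the low limit for respiratory rate, it hardly does that job. The row becomes a count of falls of 5 or more, under a label that tells the reader the resulting value is abnormally low.

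The inconsistency can be seen inside the SAP, without any outside normal range. A participant who moves from 25 to 20 is counted as low at a value that also meets the absolute limit of the high row. What is at stake is the reading of one safety table in a single-arm trial, where no control column shows how many such flags are background.

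**Working it through.** **1. The limits side by side** (all from SAP 15.4). The last column counts whole-number values strictly between the limits, which can never be flagged: high limit − low limit − 1.

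| Parameter | Low limit | High limit | Change required | Values between the limits |
|---|---|---|---|---|
| Systolic pressure | 95 | 140 | 20 | 140 − 95 − 1 = 44 |
| Diastolic pressure | 45 | 90 | 20 | 90 − 45 − 1 = 44 |
| Heart rate | 50 | 100 | 20 | 100 − 50 − 1 = 49 |
| Respiratory rate | 20 | 20 | 5 | none |

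A respiratory rate of exactly 20 meets both absolute limits. It cannot be counted in both rows for the same baseline, because it cannot be both a fall and a rise.

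**2. When the low limit has any effect.** Let *b* be the baseline and *v* the later value. The low row requires *v* ≤ 20 and *b* − *v* ≥ 5, that is, *v* ≤ min(20, *b* − 5). The limit of 20 matters only if *b* − 5 > 20, that is, if *b* > 25.

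| Baseline | Flagged low at or below |
|---|---|
| 18 | 13 |
| 20 | 15 |
| 22 | 17 |
| 24 | 19 |
| 25 | 20 |
| 26 | 20 (a value of 21 meets the fall of 5 but is excluded) |
| 30 | 20 (values 21 to 25 are excluded) |

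So up to baseline 25 the criterion is any fall of 5 or more; from 26 upward the limit does exclude some falls.

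**3. How often noise alone would be flagged.** The documents give no distribution of respiratory rate, so every input here is an assumption: baseline mean 17 or 18, between-person SD 2, whole-number readings, one baseline reading, five later visits, and no true change. As to the number of visits, vital signs are scheduled every two weeks, and the median treatment duration in the earlier phase Ib study (Protocol 2.2) was 8.9 weeks (8.9 / 2 ≈ 4.5 intervals). Five is therefore plausible, but still assumed. Simulated share of participants flagged low at least once:

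| Within-person SD | Flagged low under the SAP rule | As a number out of 141 |
|---|---|---|
| 1 | about 0.4% | 141 × 0.004 ≈ 1 |
| 1.5 to 2 | 6.6% to 18.3% | 141 × 0.066 ≈ 9 to 141 × 0.183 ≈ 26 |

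At within-person SD 1.5 to 2, about 98.4% to 99.7% of all falls of 5 or more also satisfy the limit of 20, so the limit removes almost nothing. For scale only, an arbitrary low limit of 12 would reduce the 6.6-18.3% to 0.9-6.1%. That figure shows what a working limit does; it is not a proposed value.

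**The case against.** The best case for leaving the row alone has four parts.

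- **A change-only criterion is legitimate.** Weight already has one in the same list, so it would be wrong to say that every other vital sign has separated limits; that is true of systolic pressure, diastolic pressure and heart rate. This stands, and it shapes the fix. But the respiratory-rate row is not presented as change-only. It carries a limit that appears to define a low value and does not.
- **The flagged share is mostly assumed noise.** At within-person SD 1 the problem nearly vanishes. Under the same no-change model at SD 1.5-2 the high row, whose limit is not questioned here, flags about 4-15%. This stands. The 7-18% cannot be attributed wholly to the shared limit and should not be quoted without its assumptions.
- **The consequence is small.** No test, stopping rule or endpoint uses the row, and the listing shows the actual values. This stands.
- **The criterion is joint.** A reader might infer that normal rates are flagged as such, or that the limit never filters. Neither follows: a fall of at least 5 is always needed, and the limit does exclude values from baseline 26 upward.

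A reader might also infer that these flags could hide lung toxicity, since pneumonitis is an important identified risk and the protocol reports two fatal interstitial lung disease cases. The documents do not support that. The increase row is counted separately. Pneumonitis is a programmed category of immune-related events (SAP 15.2.4.2). Oxygen saturation and the Japanese-site lung markers have their own listings (SAP 15.4 and 15.3). None of these uses the low respiratory-rate limit.

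**Conclusion.** The low respiratory-rate criterion is wrong as written. That the limits coincide, and that the low limit is idle up to baseline 25, follows from SAP 15.4 alone and needs no assumption. To call the flagged rates ordinary needs an assumed adult range, which the documents do not give; the 25-to-20 example makes the point without one.

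The effect is limited to one row of one descriptive safety table. The increase row, the listings, the pneumonitis and interstitial lung disease analyses and the efficacy analyses are unaffected. How many participants would be mislabelled is uncertain: from almost none to roughly one in six, depending mainly on the assumed within-person variability. This is a small correction, worth making because the row would otherwise mislead and the remedy is cheap.

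**What to change.** Before the table is programmed, check the low respiratory-rate limit in SAP 15.4 against the sponsor's vital-sign standard and replace it with a value below the high limit, as for the blood pressures and heart rate. The documents supply no such value, so none is suggested here.

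If the sponsor has no low limit, keep the row but drop the absolute limit and label it as a change-only criterion (fall of 5 or more breaths/min), in the same form as the weight rows. This is better than deleting the row, which would remove a prespecified safety summary.

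The cost is one number, or one relabelled row, in the SAP and in the program. No data collection changes.
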